Statistical analysis plan.

Study name: The use of Focused Lung Ultrasound in Patients Suspected of COVID-19.

8.April 2020

Descriptive data:		
Demographic	Age	Mean, sd
	Sex	% kvinder
	Weight	Mean, sd.
	Height	Mean, sd.
	Site	groupe
Baseline data	BT sys	Mean, sd.
	BT dia	Mean, sd.
	SAT	Mean, sd.
	Puls	Mean, sd.
	Respiratory Rate	Mean, sd.
	Oxygen, l/min	Mean, sd.
	ferritin	Mean, sd.
	Hbg	Mean, sd.
	Leukocytter	Mean, sd.
	Lymfocytter	Mean, sd.
	Mono	Mean, sd.
	Neutrofile	Mean, sd.
	Egfr	Mean, sd.
	Karbamid	Mean, sd.
	Kreatinin	Mean, sd.
	Natrum	Mean, sd.
	Kalium	Mean, sd.
	Ddimer	Mean, sd.
	Probnp	Mean, sd.
	Tnt	Mean, sd.
	Tni	Mean, sd.
	glucose hba1c	Mean, sd.
	ph	Mean, sd.
	pco2	Mean, sd.
	po2	Mean, sd.
	be	Mean, sd.
	bicarbonat	Mean, sd.
	lactat	Mean, sd.
	Rtg af thorax	Grupper
	CT thorax	Grupper
	Covid-19 pcr	Yes/No
Treatment data	Antibiotica	Yes/No
	Antiviral	Yes/No

	Biological	Yes/No	
	Anti thrombotic	Yes/No	
	Death during admission	Yes/No	
	Length of admission	kontinuert	
	Death at 30 days	Yes/No	
	Cause of death	Covid/ikke-covid	
	Treatment restrictions, ITA	Yes/No	
	Treatment restrictions, ventilator	Yes/No	
FLUS data.	L1	0-3	
	L2	0-3	
	L3	0-3	
	L4	0-3	
	L5	0-3	
	L6	0-3	
	L7	0-3	
	R1	0-3	
	R2	0-3	
	R3	0-3	
	R4	0-3	
	R5	0-3	
	R6	0-3	
	R7	0-3	
	Flus mean	0-3, sd	
Inter- intraobservatør agreement			
Limits of agreement. Bland altmann.		20% Flus film re-scored by 1.observatør	Weigthed kappa kap s1 s2, tab wgt(w)
		20% Flus film scored by 2.observatør	Weigthed kappa kap o1 o2, tab wgt(w)
Mean Flus score related to event:			
Covid death	Parametric distribution qq plot and histogram		
	Norm +	t-test.	ttest flusmed, by(covdod)
	Norm -	Wilcoxon	ranksum flusmed, by(covdod)
			by covdod, sort : summarize flusmed, d graph bar (Mean) flusmed, over(covdod)
ITA admission	Parametric distribution qq plot and histogram		
	Norm +	t-test.	ttest flusmed, by(ita_in)
	Norm -	Wilcoxon	by ita_in, sort : summarize flusmed, d ranksum flusmed, by(ita_in)

			graph bar (Mean) flusmed, over(ita_in)
Ventilator treatment	Parametric distribution qq plot and histogram		
	Norm +	t-test.	ttest flusmed, by(respirator_beh)
	Norm -	Wilcoxon	by respirator_beh, sort : summarize flusmed, d ranksum flusmed, by(respirator_beh) graph bar (Mean) flusmed, over(respirator_beh)
Prædiction of event			
Covid death	Univariat logistical regression	Variable: covdod flusmed	
	Multivariate logistical regression	Variable: covdod, Flusmed, alder, køn, sat, ilt (kategori?)	
ITA admission	Univariat logistiscal regression	Variable: ita_in flusmed	
	Multivariate logistical regression	Variable: ita_in, Flusmed, alder, køn, sat	, if behandlingsloft_ita ==0
Ventilator treatment	Univariat logistical regression	Variable: respirator_beh flusmed	
	Multivariate logistical regression	Variable: respirator_beh Flusmed, alder, køn, sat	, if behandlingsloft_resp ==0

Continuous variables are assessed for parametric distribution with quartile-quartile plots. Medians, interquartile ranges or means and standard deviations and ranges are reported according to parametric distribution. Students' t-test or Mann-Whitney U test is used as it was considered appropriate to evaluate differences between groups. The statistical significance is set to 5%. All data are handled in Excel (Microsoft) and REDCap (hosted at Aarhus University). All analyses are performed using Stata 14.2 (StataCorp, USA).

Building Prediction Models

Prediction models are based on multivariable logistic regression and preselected variables. The variables are sex, age, relevant comorbidity, oxygen administration and the mean-FLUS score. The selection of these variables is based on published data and clinical experience available to the study group during the study design stage. Explanatory variables are examined to decide cut-points, scales or the need for transformation. Variables are limited and prioritized to avoid overfitting or underfitting, respecting the study population size. Every included variable require at least 15 events.

The dependent variable is the primary outcome of interest: the COVID-19-related need for mechanical ventilation in the main analysis. Secondary outcomes are analyzed using the same logistic regression model, except for the outcome on high-flow oxygen treatment. The explanatory variable on oxygen administration is considered closely related to the outcome and is thus excluded from this analysis.

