Binary endpoints, including primary endpoint, are analyzed using Chi-2 test. Continuous data are assessed for parametric distribution and analyzed with Student's T-test on logarithmic transformed data in case of non-parametric distribution.

Level of statistical significance is set to 5%.

A logistic prediction model will be developed. Dependent variable is intubation. Independent variables are age (continuous), FLUS result (Binary or ordinal), SARS-CoV-2 status (Binary) and peripheral oxygen saturation (continuous).

The data set will be divided in two. One is used for model development and one is used for validation of the model. Geographic external validity is tested. Internal validity is tested with bootstrapping method. Sensitivity, specificity and ROC AUC is calculated.

Sample size

No prior publications are available for sample size estimation.

For the prediction model we wish to include 10-15 events per independent variable, 50-75 events. From early estimations about 20% of admitted patients requiring intubation our estimate is 375-400 participants.

Inclusion period

An end date is set to May 15 2020. If COVID-19 pandemic is ongoing at this time point the study may extent.

Blinding

Ultrasound film clips are analyzed blinded to other variables.

Plan for publication

Data analysis is estimated to end July 1. 2020. Article submission is estimated to October, 2020.

Preliminary data analysis

Available data will be analyzed soon after 15. May.

Ethical considerations

FLUS is without any risk to patients. COVID-19 is an infectious disease and isolation is needed. Contamination during the study needs to be avoided. For this reason, FLUS is only performed by the physicians who are required to see the patient regardless of this study. The ultrasound equipment is cleaned after each examination in accordance with local guidelines.

Legal regulations

In Denmark the study is classified as a quality assurance project. Arrangements and permission to access to patient files in each site is required. According to guidance from the legal office at Region Midt a data management agreement is not needed.

International data agreements are required to data transfer from international sites to Denmark.

All international sites must adhere to local regulation. Responsibility of this is on the international site.

Publication

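### The three mean-FLUS t-tests pool one variance across groups that, for ventilation, are expected to be about 1:4; an unequal-variance test would be a minor, nearly free improvement

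*SAP*

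**What the plan says.** In the SAP table under 'Mean Flus score related to event', each of three events has two branches. If the Q-Q plot and histogram look normal ('Norm +'), a t-test is run; if not ('Norm -'), a Wilcoxon rank-sum test. The t-test commands are "ttest flusmed, by(covdod" for COVID death, "ttest flusmed, by(ita_in" for ITA (intensive care) admission and "ttest flusmed, by(respirator_beh" for ventilator treatment (closing brackets omitted). None carries `unequal` or `welch`. The fallback for ventilation is "ranksum flusmed, by(respirator_beh".

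The SAP text after the tables agrees with the commands. On the test it says: "Students' t-test or Mann-Whitney U test is used as it was considered appropriate to evaluate differences between groups". On the check: "Continuous variables are assessed for parametric distribution with quartile-quartile plots". On software: "All analyses are performed using Stata 14.2 (StataCorp, USA". In that software the two-sample `ttest` pools the variances unless told otherwise, so the command and the named Student's test describe the same analysis.

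The group sizes follow from the protocol's 'Sample size' section: "From early estimations about 20% of admitted patients requiring intubation our estimate is 375-400 participants".

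**The concern.** The pooled t-test assumes one common variance. When groups are equal in size, it tolerates a violation well. When one group is four times the other, the pooled variance is dominated by the larger group, while the uncertainty of the difference comes mostly from the smaller one. If the smaller (event) group is the more variable, the standard error is too small, so intervals are too narrow and p-values too low. If it is the less variable, the standard error is too large and power is lost.

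The plan contains no safeguard. A Q-Q plot and a histogram examine shape, and two roughly normal groups with different SDs pass to the pooled test. Unequal spread is plausible because mean FLUS is bounded at 0 and 3, and on such a scale the SD tends to move with the mean. At stake are the interval and p-value for the unadjusted FLUS difference.

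**Working it through.** **Inputs**
- Events, participants and rate (protocol, 'Sample size'): 50-75 events, 375-400 participants, about 20% intubated.
- Significance level (SAP text): 5%; two-sided is assumed.
- SD of mean FLUS in each group: not given. The ratio r = SD(event) / SD(non-event) is therefore an assumption, varied below.

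**Group sizes.** 75 / 0.20 = 375, which reproduces the lower stated figure. 400 × 0.20 = 80. The ventilation comparison is thus 75 v 300 to 80 v 320, or 1:4. The cohort also takes patients seen only for diagnostic work-up, so the realised ratio could be more unequal.

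**Formula.** With the non-event SD set to 1, n1 = 75 and n0 = 300:
- pooled variance = [(n1 − 1)r² + (n0 − 1)] / (n1 + n0 − 2)
- pooled SE = √[pooled variance × (1/n1 + 1/n0)]
- true SE = √[r²/n1 + 1/n0]
- actual error = 2 × [1 − Φ(1.966 × pooled SE / true SE)]

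**Example, r = 1.5.** Pooled variance = (74 × 2.25 + 299) / 373 = 1.248. Pooled SE = √(1.248 × 0.01667) = 0.144. True SE = √(0.0300 + 0.0033) = 0.183. Then 1.966 × 0.144 / 0.183 is about 1.55, and the error is 12.0%.

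**Type I error with equal means** (nominal 5%; 40,000 simulated normal data sets per setting)

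| Groups | r | Formula | Pooled, simulated | Welch, simulated |
|---|---|---|---|---|
| 75 v 300 | 0.67 | 1.3% | 1.3% | 5.0% |
| 75 v 300 | 0.8 | 2.5% | 2.6% | 5.2% |
| 75 v 300 | 1.0 | 4.9% | 5.1% | 5.1% |
| 75 v 300 | 1.25 | 8.5% | 8.5% | 4.9% |
| 75 v 300 | 1.5 | 12.0% | 12.0% | 5.0% |
| 188 v 187 | 1.5 | 4.9% | 5.1% | 5.1% |

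The last row shows that the effect comes from imbalance combined with unequal spread, not from unequal spread alone.

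**Interval coverage with different means.** The same formula gives 1 − error as the coverage of a nominal 95% pooled interval: 93.7% at r = 1.1, 92.2% at 1.2 and 89.3% at 1.4. Simulating a bounded 0-3 score (beta distribution, same dispersion parameter in both groups, 75 v 300) agrees:
- means 0.8 and 1.2 (r = 1.11): about 93.5%
- means 0.5 and 0.8 (r = 1.19): about 92%
- means 0.4 and 1.2 (r = 1.44): about 88%

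The unequal-variance interval covers about 95% in each. The means are assumptions.

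**Power.** At r = 0.67 and a true difference of 0.25 non-event SDs, power is 54% pooled and 73% Welch. At equal SDs and a difference of 0.3 SD, it is 63.9% pooled and 63.5% Welch.

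**Rank-sum fallback.** Read as a test of location at 75 v 300 (5,000 data sets), it rejects 2.0% at r = 0.5 and 8.0% at r = 1.5, so it is not fully robust to unequal spread either.

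**The case against.** A reader might infer that the 5% level of these tests is shown to fail. The documents do not support that. The 9% and 12% figures need equal means together with SDs that differ by 25-50%, and nothing in either document gives a reason to expect that combination. The reason for expecting unequal spread, a score bounded at 0, operates through different means, and then type I error is not in question. In the bounded-score run with means 0.4 and 1.2, both tests reject in every simulated study. This objection stands: the realistic harm is interval coverage or lost power.

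A reader might also apply 1:4 to all three comparisons. Only the ventilation figure has a source; no event rate is given for ITA admission or COVID death.

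Second, the SAP's own branching removes some of the worst cases. A non-event group piled up near 0 is visibly skewed (skewness about 1.3 to 1.7 in the runs at r = 1.44) and should go to the rank-sum test. This stands in part. Milder cases, with r near 1.1 and skewness about 0.6 to 0.8, could still be judged normal, and the coverage loss there is about one percentage point.

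Third, nothing decisive rests on these tests. The protocol's primary endpoint uses a Chi-2 test on binary FLUS, and the SAP's main analysis is a logistic model. This also stands. Moreover, the SAP's univariate logistic regression of ventilation on mean FLUS shares the weakness: with equal means and r = 1.5, its Wald test rejected about 11-12% of the time in simulation, and changing the t-test does not alter that.

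Finally, Student's test after a look at the distribution is conventional practice. True, but the alternative is at least as good in every setting examined, apart from a trivial power difference when the SDs are equal.

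**Conclusion.** The point holds as a minor improvement to secondary, unadjusted comparisons. The pooled test is what the SAP specifies, no step checks equality of variance, and for ventilation the protocol implies about 75 v 300. Under those sizes a pooled 95% interval would cover about 94%, 92% or 88% at SD ratios of 1.1, 1.2 or 1.4. If the event group is the less variable, the cost is power. Type I error is displaced only if the means are equal while the SDs differ.

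All of this rests on assumed SD ratios: neither their size nor their direction is in the documents, so neither inflation nor conservatism can be asserted. The primary Chi-2 test and the logistic models are not affected.

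**What to change.** Add `unequal` (or `welch`) to the three `ttest` commands under 'Mean Flus score related to event'. In the SAP text, replace Student's t-test with the unequal-variance (Welch) t-test. Report each mean difference with its unequal-variance 95% confidence interval, beside the group SDs.

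The cost is one word in three commands and one phrase in the text, with a power difference of 63.9% v 63.5% if the SDs turn out equal. The change does not correct the univariate logistic p-value and should not be presented as doing so.

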FLUS can diagnose COVID-19 pneumonia with high sensitivity and specificity using PCR-test and chest radiograph as reference.

Aim

To study the ability of FLUS in COVID-19 to predictive respiratory failure.

To study the diagnostic capability of FLUS to find COVID-19 pneumonia.

To study risk-stratifying capability of FLUS in patients with COVID-19 symptoms.

Method

Design

Multicenter prospective cohort study with convenience sampling.

Setting

Emergency departments or internal medicine departments who admit patients with COVID-19 symptoms.

Participants

Patients who have COVID-19 symptoms and require diagnostic testing.

Patients who have a positive SAR-CoV-2 PCR-test and require admission to hospital.

Inclusion criteria

- Patients who are seen in COVID-clinics or emergency departments due to symptoms that require diagnostic work-up to COVID-19.
- Patients admitted to hospital with positive SARS-COV-2 PCR-test and in whom FLUS is performed less than 48 hours after admission.

Exclusion criteria

- Age less than 18 year.
- Former participation in this study.
- Pre-FLUS ventilator support.

Double inclusion

Inclusion in this study will not restrict patient from inclusion in other studies.

Recruitment

Participants are recruited at the local hospital. In Denmark the study is labelled quality assurance and the need for informed consent is thus waived. Local regulations are followed and it is the responsibility of each inclusion site to achieve appropriate regulatory permissions including need for approval from local ethical committees and healthcare authorities.

Variables

Ultrasound variables: FLUS are performed according to ERS guidelines and to Standard of Operating Procedure specific to this study. Film clips are recorded and saved for later evaluation. 14 zones are scanned. Film clips are marked with scanning position (L1, L2...etc.). If the patient is unable to sit, only anterior and lateral zones are scanned. FLUS findings are assessed on the film clips by an observer blinded to other variables. Findings are coded with 1/0 for presence of pneumonia. Moreover, a scoring system is applied:

FLUS findings	Score
Normal FLUS	0
Interstitial syndrome, defined as more than 3 B-lines in a single zone.	1
Diverse B-lines or irregular pleura	
Interstitial syndrome, defined as more than 3 B-lines in a single zone.	2
Confluent B-lines.	
Consolidations (sub-pleurale, lobar, with or without air-bronchograms)	3

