Data on FLUS operator: Level of medical degree. Years of experience with lung ultrasound. Completed training in FLUS.

From patient files the following data is extracted:

Patient demographic: Sex, age, height, weight, co-morbidities.

Clinical data on time of admission: Blood pressure, pulse, peripheral saturation, respiratory frequency, temperature, length of illness, list of symptoms, limitation to treatment i.e. not suited or willing to intensive care treatment and intubation.

Data from radiographic diagnostics: Result of chest radiograph, CT or HRCT scanning, if done for clinical reasons. No further review of radiographic examinations is performed. Results given by local radiology department is used.

Microbiological data: Result of SARS-CoV-2 PCR-test from nasal/oral/laryngeal or tracheal samples.

Data from admission: Time of admission. Place of admission. Time of dismissal. Admission to intensive care. Intubation. Time in ventilator. Death, survival. In hospital survival, 14- and 30-days survival.

Endpoints

Primary endpoint: FLUS (binary: positive/negative pneumonia) related to intubation (yes/no).

Secondary endpoints: Relationship between FLUS and SARS-CoV-2 PCR result.

Relationship between FLUS and radiographic findings.

Relationship between FLUS and admission to intensive care (not intubation).

Relationship between FLUS and re-admission (Patient returning to emergency department or COVID-clinic).

Scores of FLUS findings in different zones.

Data management

The study uses convenience sampling as FLUS may not be available at all times. FLUS is performed by the clinician such that only doctors with clinically relevant work are allowed to scan the patient. This minimizes the risk of disease transfer to doctors and reduces the use of protection equipment.

Ultrasound film clips are recorded according to standard operating procedure. Film clips are stored securely, according to local legal regulations. All variables extracted from patient files are stored in an eCRF using REDCap supplied by Aarhus University Hospital.

Every site will have access to enter data in data capture instruments. Access to REDCap is managed by the project steering committee at Aarhus University Hospital.

Data analysis

All data are analyzed in Stata.

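### The SAP text's main outcome (COVID-19-related ventilation, no SARS-CoV-2 term) does not fit a cohort that includes PCR-negative patients, and conflicts with the protocol and the SAP's own table

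*SAP*

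**What the plan says.** **Population.** The protocol's Inclusion criteria give two routes of entry. The first is "Patients who are seen in COVID-clinics or emergency departments due to symptoms that require diagnostic work-up to COVID-19". The second is "Patients admitted to hospital with positive SARS-COV-2 PCR-test and in whom FLUS is performed less than 48 hours after admission". The first route brings in patients who turn out PCR-negative. The stated aim covers them too: "To study risk-stratifying capability of FLUS in patients with COVID-19 symptoms".

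**Protocol outcome and model.** The Endpoints section has "Primary endpoint: FLUS (binary: positive/negative pneumonia) related to intubation (yes/no". For the prediction model, the Data analysis section says "Dependent variable is intubation", and the covariates are age, FLUS result, "SARS-CoV-2 status (Binary) and peripheral oxygen saturation (continuous"). Neither outcome carries a COVID-19 qualifier.

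**SAP text.** Under Building Prediction Models the dependent variable is "the COVID-19-related need for mechanical ventilation in the main analysis". The five explanatory variables are sex, age, comorbidity, oxygen administration and mean FLUS score. SARS-CoV-2 status is not among them, the model is not limited to PCR-positive patients, and relatedness to COVID-19 is not defined.

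**SAP table.** The ventilation rows use `respirator_beh`, labelled as ventilator treatment with no COVID-19 qualifier. The multivariable version has mean FLUS, age, sex and saturation, and its only filter is on ventilator treatment limits (`behandlingsloft_resp ==0`). The table splits COVID from non-COVID only for cause of death.

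**The concern.** The plan holds three versions of its main outcome, and the SAP text's version fits the enrolled population worst. In a binary logistic model without a PCR restriction, a ventilation not attributed to COVID-19 has no obvious code other than 0. Two things follow.

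First, real ventilations leave the outcome. A PCR-negative patient with another pneumonia, a positive scan and later ventilation counts as a false positive, although the scan flagged the failure. That works against the aim of stratifying risk in everyone who presents with symptoms.

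Second, with SARS-CoV-2 status left out, FLUS can absorb the contrast between COVID-19 and other disease. The protocol expects FLUS to carry that contrast: "FLUS can diagnose COVID-19 pneumonia with high sensitivity and specificity using PCR-test and chest radiograph as reference". The estimate would then be read as prognosis when part of it is diagnosis.

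The missing attribution rule adds a further uncertainty. If relatedness is a clinical judgement, the treating physician already has the bedside scan result.

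**Working it through.** **The plan's own figure.** The protocol's Sample size section wants 10–15 events per variable, 50–75 events in all, at about 20% intubation among admitted patients. 5 × 15 = 75 events, and 75 / 0.20 = 375, the lower stated size. At 400, 400 × 0.20 = 80 events. The 20% applies to admitted patients, so it describes neither the whole symptomatic cohort nor COVID-19-related ventilation within it.

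**Illustration: inputs.** The documents give no PCR-positive share, no ventilation rate in PCR-negative patients and no FLUS positivity by PCR status, so these are assumptions. There are 400 patients, 200 PCR-positive and 200 PCR-negative. FLUS is positive in 70% and 30%, and ventilation occurs in 20% and 5%. Within each PCR group FLUS has no prognostic value. COVID-19-related ventilation means ventilation in a PCR-positive patient; all other ventilations are coded 0.

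| | FLUS positive | FLUS negative |
|---|---|---|
| PCR-positive patients | 140 | 60 |
| PCR-negative patients | 60 | 140 |
| Total | 200 | 200 |
| Ventilated, PCR-positive (20%) | 28 | 12 |
| Ventilated, PCR-negative (5%) | 3 | 7 |
| Ventilated, all | 31 | 19 |

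- COVID-19-related: OR = (28/172) / (12/188) = 2.55.
- All-cause, crude: OR = (31/169) / (19/181) = 1.75.
- All-cause, by SARS-CoV-2 status: 28/140 against 12/60 (both 20%) and 3/60 against 7/140 (both 5%), so the adjusted OR is 1.00.
- Ventilations recoded as non-events: 3 + 7 = 10 of 50.

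**Range.** With 30–70% PCR-negative and 2–10% ventilation among them, keeping 70% versus 30% FLUS positivity, the crude OR is 1.83–3.47 for COVID-19-related and 1.28–2.46 for all-cause ventilation. Between 2 and 28 events are recoded.

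**Sensitivity to FLUS positivity (base case otherwise).**
- 70% in both groups: 280 FLUS-positive with 28 events, 120 FLUS-negative with 12. OR = (28/252) / (12/108) = 1.00; all-cause is also 1.00.
- 70% versus 60%: OR = (28/232) / (12/128) = 1.29; all-cause (34/226) / (16/124) = 1.17.
- 60% versus 70%: OR = (24/236) / (16/124) = 0.79.

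**When FLUS does have prognostic value.** Take the score as normal with SD 1, shifted by a in COVID-19 and by b in patients later ventilated. AUC is the weighted mean of Φ((m₁ − m₂)/√2) over event and non-event pairs. The PCR-positive share runs over 30–75%; ventilation is 20% in PCR-positive and 5–20% in PCR-negative patients (all assumed).

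| a, b | AUC, all-cause | AUC, COVID-19-related |
|---|---|---|
| 1, 0 (COVID-19 only) | 0.50–0.60 | 0.58–0.69 |
| 0.5, 1 (both) | 0.75–0.79 | 0.78–0.82 |
| 0, 1 (ventilation only) | 0.76 | 0.72–0.76 |
| −0.5, 1 (higher in other disease) | 0.71–0.76 | 0.63–0.72 |

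The first two rows show inflation, the last two deflation.

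**Events.** With half the cohort PCR-positive, 400 × 0.5 × 0.20 = 40 COVID-19-related events, below the protocol's target of 50–75.

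**The case against.** The strongest reply is that no passage states how a ventilated PCR-negative patient is coded. The SAP table's outcome is plain ventilator treatment, and on that reading no ventilation is recoded. This stands as far as it goes: non-event coding is an inference from the text. It does not dispose of the point. Table and text still disagree, the text calls its outcome the primary one, and the table's model also lacks a SARS-CoV-2 term, so the crude pooling effect (1.75 in the illustration) remains.

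The size of the illustration also needs care. ln 1.75 / ln 2.55 = 0.56 / 0.94, about 60% of the log odds ratio, so most of the effect comes from pooling two groups and not from the outcome rule. With 30% PCR-negative and 2% ventilation among them the gap is only 1.83 against 1.68. These are crude odds ratios for a binary scan, whereas the SAP adjusts a mean score for other variables. All of this stands.

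A cause-specific outcome is legitimate and fits the hypothesis about respiratory failure in COVID-19 pneumonia. That hypothesis, however, concerns patients with COVID-19, and the SAP does not restrict the model to them. Blinded reading of the clips protects the score, but not a clinical judgement of relatedness. Whether such a judgement would be used is unknown.

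A reader might infer two stronger claims. One is that FLUS is rewarded for detecting COVID-19 instead of predicting respiratory failure. The documents do not support this: the direction depends on FLUS positivity by PCR status, both signals can contribute, and FLUS can be penalised. The other is that the SARS-CoV-2 term would have an event-free category and break the fit. That joins the protocol's covariate to the SAP's outcome, a model neither document plans.

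**Conclusion.** The point holds in conditional form and should be settled before analysis. The conflict between the protocol, the SAP text and the SAP table is plain from the documents. So is the loss of the SARS-CoV-2 covariate between the protocol and the SAP. The bias is conditional on two things: that the SAP text governs, and that ventilations not attributed to COVID-19 are coded as non-events. Real ventilations are then lost whatever the direction of the bias. Inflation is the direction the protocol's own diagnostic hypothesis predicts, but it is not established. The odds ratios and AUCs show what the definition can do under assumed inputs; they do not estimate what it will do in this cohort.

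**What to change.** 1. Reconcile the three outcome definitions. In the whole cohort, make all-cause mechanical ventilation the main outcome, and state that the protocol's intubation yes/no and the SAP table's `respirator_beh` are the same event.
2. Put SARS-CoV-2 status back in the main model. Changing the outcome alone is not enough: the crude all-cause OR in the illustration is still 1.75, and only adjustment brings it to 1.00.
3. Replace the undefined COVID-19-related judgement with a second model of ventilation restricted to PCR-positive patients.

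The cost is SAP wording and one extra model on data already collected. The sixth variable also counts against the SAP's rule of 15 events per variable: 6 × 15 = 90 events, against 5 × 15 = 75 for its present list. In the illustration there are 50 all-cause events, and 50 / 15 supports three variables; the PCR-positive model has 40, and 40 / 15 supports two. The SAP already says variables will be limited and prioritised, so that order should be written down now. The FLUS effect may look smaller than under the present text.

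### The high-flow oxygen model drops baseline oxygen for an invalid reason and is left with no physiological measure of respiratory status

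*SAP*

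**What the plan says.** The SAP, under Building Prediction Models, fixes the predictors in advance: "The variables are sex, age, relevant comorbidity, oxygen administration and the mean-FLUS score". Mechanical ventilation is the outcome of the main analysis. For the rest, "Secondary outcomes are analyzed using the same logistic regression model, except for the outcome on high-flow oxygen treatment", and the reason follows: "The explanatory variable on oxygen administration is considered closely related to the outcome and is thus excluded from this analysis".

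The SAP's analysis table gives different lists. Its multivariable rows are "respirator_beh Flusmed, alder, køn, sat" for ventilator treatment and "ita_in, Flusmed, alder, køn, sat" for intensive care. The row for COVID death also has saturation and adds oxygen, with a question mark over categorising it. (In the Danish labels, alder is age, køn is sex, sat is saturation and ilt is oxygen.) The table has no row for high-flow oxygen.

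The protocol, under Data analysis, plans one logistic model, for intubation: "Independent variables are age (continuous), FLUS result (Binary or ordinal), SARS-CoV-2 status (Binary) and peripheral oxygen saturation (continuous". High-flow oxygen is not among the protocol's endpoints.

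Respiratory status at baseline is recorded. The protocol's admission data include "Blood pressure, pulse, peripheral saturation, respiratory frequency, temperature, length of illness", and the SAP's baseline list has saturation, respiratory rate and oxygen flow in l/min.

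**The concern.** The prose is the only specification for the high-flow outcome. Once oxygen is removed, mean FLUS stands beside age, sex and comorbidity, with no saturation, respiratory rate, blood gas or oxygen flow.

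The stated reason does not support the removal. A variable measured before the outcome and strongly related to it is what a new predictor should be tested against. Removal is justified where the variable already contains the outcome. Here that means patients receiving high flow when they are scanned, and the SAP does not say how they are handled.

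The interpretation of FLUS is at stake. The protocol wants to know whether FLUS can risk-stratify patients. An adjusted odds ratio for high-flow treatment will be taken as information beyond what is known at the bedside. Without a respiratory covariate it cannot carry that meaning.

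**Working it through.** **1. Predictor lists side by side**

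| Source | Outcome | Oxygen | Saturation |
|---|---|---|---|
| SAP prose | ventilation, most secondary outcomes | yes | no |
| SAP prose | high-flow oxygen | removed | no |
| SAP table | ventilator, intensive care | no | yes |
| SAP table | COVID death | yes (form open) | yes |
| Protocol | intubation | no | yes |

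Every multivariable model except the high-flow one has at least one physiological respiratory covariate. The prose and table lists also conflict with each other.

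**2. How much could move to FLUS**

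The documents give neither the FLUS–oxygen correlation nor the effect of oxygen, so every input here is an assumption:
- event rate 20%
- oxygen odds ratio 2 or 3 per SD
- age coefficient 0.3 per SD, age correlated 0.1 with the other variables
- saturation (coded so that higher is worse) correlated 0.5 with oxygen, correlated with FLUS as oxygen is, and with no effect of its own

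As an approximation, the FLUS log odds ratio without oxygen is the true one plus (oxygen log odds ratio) × (slope of oxygen on FLUS given age). At correlation 0.3 the slope is (0.3 − 0.1 × 0.1)/(1 − 0.1²) = 0.29/0.99 = 0.293. With no true FLUS effect:
- oxygen odds ratio 2: exp(0.693 × 0.293) = exp(0.203) = 1.23
- oxygen odds ratio 3: exp(1.099 × 0.293) = exp(0.322) = 1.38

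Simulation (200,000 patients per setting) gave 1.21 and 1.32. The values are lower because logistic odds ratios shrink when a strong predictor is left out. The table shows all settings with no true FLUS effect. The last two columns come from 600 resamples of 375 patients per setting.

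| FLUS–oxygen correlation | FLUS OR per SD, oxygen dropped | Saturation kept instead | p < 0.05, oxygen dropped | p < 0.05, oxygen kept |
|---|---|---|---|---|
| 0 | 0.98–1.00 | 0.99–1.00 | 5–6% | 5–7% |
| 0.2 | 1.14–1.20 | 1.07–1.10 | 14–28% | 2–4% |
| 0.3 | 1.21–1.32 | 1.11–1.17 | 27–56% | 4–6% |
| 0.5 | 1.39–1.62 | 1.24–1.39 | 69–94% | 4–5% |

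With oxygen kept, the FLUS odds ratio was 0.99–1.01 throughout.

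With a true FLUS odds ratio of 1.5, dropping oxygen gave 1.77–1.87 at correlation 0.3 and 2.03–2.28 at 0.5, but 1.41–1.47 at zero correlation. Discrimination also falls: at correlation 0.3 with no true FLUS effect, the AUC went from 0.70–0.77 with oxygen to 0.61–0.62 without it.

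**3. Does a fuller model fit the planned size?**

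The plan's own figure first. The protocol wants 10–15 events per variable and 50–75 events, which implies five variables. At 20% intubated, 75/0.20 = 375, the lower end of its 375–400. (50/0.20 = 250 lies outside that range.)

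The SAP requires at least 15 events per variable. Counting one parameter per variable:

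| High-flow model | Terms | Events | N at assumed 20% |
|---|---|---|---|
| As written | 4 | 60 | 300 |
| Plus one respiratory measure | 5 | 75 | 375 |
| Plus oxygen and saturation | 6 | 90 | 450 |

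The high-flow event rate is not given. At 10%, 20% or 30%, 75 events need 750, 375 or 250 participants. With 375–400 participants, five terms need a rate of 20.0–18.75% (75/375, 75/400) and six need 24.0–22.5% (90/375, 90/400).

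**The case against.** The strongest defence is that the exclusion has a legitimate core. The prose defines neither the timing nor the device coverage of the oxygen variable. If it includes high flow at the scan, it is partly the outcome, and leaving it out is reasonable. This stands for those patients only. Restricting the model to patients not on high flow removes the overlap without removing the covariate.

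It can also be said that saturation appears in the SAP table and the protocol model. That is true, but neither covers high-flow treatment, so they do not fill the gap.

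Four stronger readings are tempting and are not supported:
- *The FLUS odds ratio is biased upward.* Only the part of the oxygen effect that is correlated with FLUS moves. At zero correlation nothing moves, and a true effect is slightly weakened. Direction and size are conditional.
- *No measure of severity remains.* Mean FLUS itself reflects lung involvement. What is missing is a physiological measure.
- *The SAP keeps oxygen for ventilation and drops it here.* This holds for the prose only; the ventilator row of the table has saturation and no oxygen. Odds ratios for different outcomes are not directly comparable in any case.
- *Both oxygen and saturation must be in the model.* At the SAP's 15 events per variable and an assumed 20% rate, that needs 450 participants, above the planned number.

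**Conclusion.** The point holds. The SAP gives an invalid general reason for dropping a baseline predictor, and the resulting model cannot show whether FLUS adds to baseline respiratory status. The reason would be valid only for patients already on high flow at the scan.

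The size cannot be fixed from the documents. The simulated odds ratios illustrate the mechanism and are not estimates for this study. They depend on the assumed correlation, the assumed oxygen effect and a 20% event rate. A positive correlation is plausible because both variables reflect lung involvement.

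The scope is one secondary model, for an outcome outside the protocol's endpoint list. The ventilation analysis is unaffected. The change is worth making before the data are analysed, but it does not threaten the study's main conclusion.

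**What to change.** Replace the exclusion sentence in the SAP with wording to this effect: *The high-flow model is fitted for new high-flow treatment after FLUS, in patients not receiving high flow at the scan. It contains age, sex, comorbidity, mean FLUS and one baseline respiratory measure. A second respiratory measure is added only if there are at least 15 events per variable. The model without a respiratory measure is reported as a sensitivity analysis.*

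Name the measure in advance: oxygen flow in l/min, or saturation as in the SAP table and the protocol model. In the simulation saturation removed only part of the inflation, but it was assumed there to have no effect of its own. Add a high-flow row to the table and reconcile the table's predictor lists with the prose.

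The costs are one more model term, fewer patients in the model and probably a smaller FLUS odds ratio. At an assumed 20% rate the margin is thin: 400 participants allow 25 exclusions (400 − 375) before expected events fall below 75, and 375 allow none. The protocol's division of the data into development and validation sets would reduce the events available for fitting further.

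The respiratory covariates are already listed as baseline data. High-flow status at the scan and the time high flow started are in neither variable list, so the sponsor should confirm that the eCRF holds them or can take them from patient files.
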